**NCT05576987**

**Study Protocol and Statistical Analysis Plan**

**June 3, 2022**

## **Introduction**

An accident is defined as an event that ends with an injury or an unexpected event that requires emergency medical attention and results in a syndrome that includes events such as trauma, fracture, poisoning, and burns (Gambarte et al., 2014). Accidents are an important public health problem due to deaths, temporary or permanent disability. Injuries are among the leading causes of death and lifelong disability between the ages of 5-14 years (WHO). Children in this age group spend certain hours of the day at school, and children are also very active physically in school. This physical activity can cause accidents and injury to the child. It is reported that 15% of child accidents occur at school (Gambarte et al., 2014). In an epidemiological study examining school accidents between 2012 and 2016 in our country, 7042 school injury records were examined. In this study, it was determined that most of the school injuries were caused by falling (60.1%) and occurred during break time (38.6%), while 13.3% of the injuries were caused by environmental reasons and 86.7% by behavioral reasons (Şengel et al., 2020). In this direction, changing the behaviors that cause injury and improving the behavior towards preventive safety measures can reduce the risk of injury due to accidents. It is identified three levels of impact in injury prevention, each of which may be appropriate for different prevention approaches. These; the internal level at which interventions can target self-efficacy, knowledge, skills and beliefs; the interpersonal level at which the intervention can target social/peer influences and norms, and the community level, which includes interventions involving the environment or settings and policies. The health belief model is among the most widely applied individual-level (internal and interpersonal) behavioral change theories in injury prevention (Orton et al., 2016). The Health Belief Model (Gözüm and Çapık, 2014), developed by Rosenstock in 1966 and later expanded by Becker et al., focuses on individuals' attitudes and beliefs. This model defends that health behavior is determined by an individual's personal beliefs or perceptions about a disease/health condition. In line with this model, a child perceives injury as a problem, takes it seriously, and as a result causes a positive behavioral change to prevent injury. In a study, it was determined that health belief model (HBM)-based school health education to high school students can improve students' health beliefs about injury (Cao et al., 2014). Another study found that an educational intervention based on the Health Belief Model could improve students' practice in preventing school injuries (Farhadi et al., 2014). Studies have shown that a HBM-based intervention can improve injury-related health beliefs and practices in injury prevention. However, sufficient information could not be reached about the effect of HBM-based

intervention on behavior towards security measures in primary school students. In this direction Purpose of this study is to research the impact of the education that has given towards the health belief model, for the behavior of children about precautions against school accidents. This study will provide scientific data support to the school health nurse on how to apply HBM in creating behavior change for safety measures to prevent school accidents.

## **Hypothesis**

Education for school accidents, prepared in line with the components of the Health Belief Model, affects the safety precautionary behavior of students for school accidents.

## **Primary Outcomes**

Behavior of Students for Safety Precautions in School Accidents

## **Method**

### **Study Design**

This research was designed as quasi-experimental. It has a pretest-posttest design with a control group.

### **Sample**

The behavior score averages and standard deviations of the two groups in a previous study (Dilek, 2018) and the effect size were calculated to determine the sample size of the study. Power analysis (significance level 0.05 for type 1 error, effect size 0.50, and power 0.95). (Gpower 3.1 version) was carried out. In the power analysis, the minimum number of participants was 87 in the experimental group and 87 in the control group. In this context, the research will be conducted with 100 participants in each group, taking into account the possibility that non-parametric statistics may need to be used due to the non-normal distribution of the dependent variable, incomplete and erroneous data, and absenteeism. Experimental and control groups will be selected from the branches 3rd and 4th grade. 3 branches will be selected for the experimental group and 3 branches for the control group. Branches will be determined by drawing. In order not to interfere with the education of students during the training, the groups will be designated as class branches.

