### **Statistical Analysis**

In the evaluation of the data, percentage, arithmetic mean, t-test for independent samples and t-test for dependent samples will be used. Significance level will be taken as  $p < 0.05$ .

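### The stated power of 0.95 treats pupils as independent; with 3 whole classes per arm, an unadjusted cluster-valid comparison does not reach it

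*Combined protocol and SAP*

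**What the plan says.** The Sample section takes its effect size from an earlier study and reports "Power analysis (significance level 0.05 for type 1 error, effect size 0.50, and power 0.95". The result is: "In the power analysis, the minimum number of participants was 87 in the experimental group and 87 in the control group". The target is then raised to 100 per group. The reasons given are a possible switch to non-parametric methods "due to the non-normal distribution of the dependent variable, incomplete and erroneous data, and absenteeism".

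On allocation, the same section says "3 branches will be selected for the experimental group and 3 branches for the control group", chosen by drawing, with the groups formed as whole classes. The Intervention Arm and Control Arm sections repeat this.

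Statistical Analysis says "t-test for independent samples and t-test for dependent samples will be used", at p < 0.05 with no sidedness stated. The Hypothesis section is non-directional: the education "affects the safety precautionary behavior of students for school accidents". The document contains no ICC, design effect, cluster term or class-level analysis.

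**The concern.** Pupils in one class share a teacher, a building routine and, in the experimental arm, the same training sessions, so their scores are likely to be correlated. When whole classes are allocated, the variance of the difference between arms depends on the number of classes as well as the number of pupils. A calculation that counts 87 or 100 independent pupils per arm overstates the information available, and three classes per arm leave very few degrees of freedom to estimate between-class variation.

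This is the plan's only power statement, and it supports the only primary outcome. If 0.95 is taken at face value, a null result would be read as strong evidence against a 0.50 SD effect when the design cannot support that reading. A positive result from a pupil-level test could reflect differences between classes.

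**Working it through.** **Inputs from the document:** alpha 0.05, standardised effect d = 0.50, power 0.95, n = 87 raised to 100 per arm, k = 3 classes per arm. Average class size is m = 100/3 = 33.3.

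**Assumed, because the document gives none:** ICC 0.01, 0.02, 0.05 and 0.10; equal class sizes; d on the total-SD scale.

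**Step 1: reproduce the 87.** For independent pupils, n per arm = 2(z_alpha + z_beta)²/d².
- One-sided: 2(1.645 + 1.645)²/0.25 = 86.6, so 87. The t calculation gives 88, and 87 per arm has power 0.949.
- Two-sided: 2(1.960 + 1.645)²/0.25 = 104.0. The t calculation gives 105, and 87 per arm has power 0.91.

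From the stated inputs, 87 is therefore the one-sided, independent-pupil figure. With independent pupils, 100 per arm would give 0.97 one-sided and 0.94 two-sided. Sidedness is a separate issue from clustering, so both are shown below.

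**Step 2: add the classes.** DEFF = 1 + (m − 1) × ICC; effective n = 100/DEFF; variance of the difference = 2 × DEFF/100; noncentrality = 0.5/√variance. Example at ICC 0.05: DEFF = 1 + 32.33 × 0.05 = 2.62; variance = 0.0523; noncentrality = 0.5/0.2288 = 2.19.

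Power is given first with normal critical values (design effect only, an optimistic bound), then for a t-test of class means on 2 × 3 − 2 = 4 df (critical values 2.132 one-sided, 2.776 two-sided).

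| | ICC 0.01 | 0.02 | 0.05 | 0.10 |
|---|---|---|---|---|
| DEFF | 1.32 | 1.65 | 2.62 | 4.23 |
| Effective n per arm | 76 | 61 | 38 | 24 |
| Design effect only, one-sided | 0.92 | 0.87 | 0.71 | 0.53 |
| Design effect only, two-sided | 0.87 | 0.79 | 0.59 | 0.41 |
| Class means, 4 df, one-sided | 0.81 | 0.73 | 0.56 | 0.41 |
| Class means, 4 df, two-sided | 0.64 | 0.55 | 0.39 | 0.26 |
| Effect detectable with power 0.95, 4 df, one-sided (SD) | 0.66 | 0.74 | 0.93 | 1.18 |
| Effect detectable with power 0.95, 4 df, two-sided (SD) | 0.80 | 0.89 | 1.13 | 1.43 |

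Simulation with classes of 33, 33 and 34 agrees with the 4-df rows, with type I error 0.05. On the design effect alone, one-sided power falls below 0.95 from an ICC of about 0.005.

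**Step 3: separate the two losses.** At ICC 0.01, two-sided, the design effect takes power from 0.94 to 0.87, and estimating between-class variation on 4 df takes it from 0.87 to 0.64. At ICC 0 the 4-df test would have 0.89 one-sided and 0.75 two-sided.

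**Step 4: the planned pupil-level t-test (simulated).** Across the four ICCs, its two-sided type I error is 0.09, 0.13, 0.23 and 0.35 (one-sided 0.08, 0.10, 0.16 and 0.21). At d = 0.50 it rejects 0.91, 0.89, 0.84 and 0.79 of the time, two-sided.

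**Step 5: pre-test adjustment.** Suppose the pre-test correlates r = 0.7 with the post-test at both pupil and class level. The variance is then multiplied by 1 − 0.49 = 0.51.
- 4 df kept (two-stage analysis): 0.97, 0.93, 0.80, 0.63 one-sided; 0.89, 0.82, 0.64, 0.45 two-sided. Simulation confirms the two-sided figures, with type I error about 0.05.
- 3 df (class-level covariate fitted): 0.81, 0.73, 0.55, 0.39 two-sided.
- r = 0.7 within classes but zero between classes: 0.75, 0.59, 0.35, 0.22 two-sided (simulated).
- On 4 df, the r needed at both levels for power 0.95 is 0.66, 0.74, 0.84, 0.91 one-sided and 0.78, 0.83, 0.90, 0.94 two-sided.

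**The case against.** **The arithmetic is not wrong in itself.** The 87 follows from the stated inputs under a one-sided test of independent pupils. That is so; the fault is the independence assumption. The one-sided basis is itself an inference: the document names the software but not the test, and 0.50 may be rounded. The clustering result does not depend on it.

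**The ICC and class sizes are the reviewer's.** This is correct, and it limits confidence in any single figure. The direction is firm, because every unadjusted cluster-valid figure in the range is below 0.95 for either sidedness. If the ICC were exactly zero, the pupil-level test would be valid and one-sided power at 100 per arm would exceed 0.95. The document makes no such case.

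**The 4-df test is the reviewer's choice and causes most of the loss at low ICC.** This also stands, and Step 3 separates the two parts. The bound that charges nothing for degrees of freedom still stops at 0.92.

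**A pre-test is collected and could recover power.** It could: at r = 0.7 at both levels and ICC 0.01, one-sided power is 0.97. But Statistical Analysis plans no adjusted comparison between groups, and the document gives no correlation. If the pre-test predicts only within classes, adjustment can even lose power at ICC 0.10 (0.22 against 0.26, two-sided).

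**The planned t-test rejects more often.** It does so only by exceeding its nominal error rate.

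**Conclusion.** The concern holds. The 0.95 belongs to a design with individually independent pupils, which is not the design described. Under class allocation with 3 classes and 100 pupils per arm, an unadjusted test that keeps its 5% error rate would miss a true 0.50 SD effect with probability 0.19 to 0.59 one-sided, or 0.36 to 0.74 two-sided, against the 0.05 implied. These ranges rest on the assumed ICCs, equal classes and a class-mean test on 4 df. That the power falls short is certain over the assumed ICC range; its exact size is not. The conclusion is confined to unadjusted comparisons, since a well-correlated pre-test could close part of the gap, and at the lowest ICC one-sided all of it.

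**What to change.** In Sample, replace the 0.95 claim with the power and detectable effect for 3 classes per arm of about 33 pupils. State:

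1. the sidedness (two-sided fits the non-directional hypothesis);
2. the assumed ICC range;
3. the cluster-valid analysis the figure refers to and its degrees of freedom (4 for class means, 3 if a class-level pre-test covariate is fitted);
4. the expected gain from pre-test adjustment, with the assumed correlation at pupil and at class level.

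Name the same analysis in Statistical Analysis in place of the pupil-level between-group t-test. One option is a two-stage analysis: regress post-test on pre-test across pupils without an arm term, then compare class-mean residuals by t-test on 4 df.

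Possible wording: *Two-sided 5%, class means on 4 df: power for a 0.50 SD difference is 0.64 to 0.26 unadjusted at assumed ICC 0.01 to 0.10. With two-stage pre-test adjustment it is 0.89 to 0.45 if r = 0.7 at both pupil and class level, and 0.75 to 0.22 if the pre-test predicts only within classes.*

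This needs no extra pupils, classes or visits. It does change the primary analysis, and the stated power becomes less favourable and rests on assumed ICC and r. Rewording makes the claim accurate but does not restore the power. Keeping 0.95 for an unadjusted comparison with classes of about 33 would take 5 to 12 classes per arm one-sided, or 6 to 15 two-sided, over the same ICC range.

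### The number of sides is not stated: with the printed inputs 87 per group fits only a one-sided t-test, and on the more natural two-sided reading 100 per group holds no reserve above 0.95 power

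*Combined protocol and SAP*

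**What the plan says.** All in the combined protocol and SAP:

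- **Sample, source of the effect size.** It was worked out from "The behavior score averages and standard deviations of the two groups in a previous study". Those means and standard deviations are not reproduced.
- **Sample, inputs.** "Power analysis (significance level 0.05 for type 1 error, effect size 0.50, and power 0.95", run in G*Power 3.1. Neither the test family nor the number of tails is given.
- **Sample, result.** "the minimum number of participants was 87 in the experimental group and 87 in the control group".
- **Sample, planned size.** "the research will be conducted with 100 participants in each group, taking into account the possibility that non-parametric statistics may need to be used". Incomplete or erroneous data and absenteeism are further reasons given for the increase.
- **Hypothesis.** The education "affects the safety precautionary behavior of students for school accidents". No direction is given.
- **Statistical Analysis.** "t-test for independent samples and t-test for dependent samples will be used", with significance at p < 0.05. No one-sided test is declared.

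**The concern.** A sample size can be checked only if the number of sides is known. Here the printed minimum points one way, and the ordinary wording of the hypothesis and analysis points the other.

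Two things depend on it. The first is the reserve. The plan presents 100 per group as 87 plus cover for rank tests, unusable data and absence. If the minimum for 0.95 power is really above 100, that cover does not exist. The second is the rejection rule for the between-group comparison. A result in favour of the education can be significant on one reading and not on the other, so the choice should be fixed before data are seen.

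**Working it through.** **Inputs.** From the Sample section: alpha 0.05, d = 0.50, power 0.95, equal groups, stated minimum 87, planned size 100. Assumptions: pupils are independent, and d = 0.50 applies to the score that is compared.

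**1. Reproducing 87 by the normal approximation.** n per group = 2(z_alpha + z_power)² / d².
- One-sided: 2 × (1.645 + 1.645)² / 0.25 = 86.6, so 87.
- Two-sided: 2 × (1.960 + 1.645)² / 0.25 = 104.0, so 104.

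**2. Exact t-test.** Power comes from the noncentral t with 2n − 2 degrees of freedom and noncentrality d√(n/2). For d = 0.50:

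| n per group | One-sided power | Two-sided power |
|---|---|---|
| 87 | 0.9495 | 0.906 |
| 88 | 0.951 | 0.910 |
| 90 | 0.955 | 0.916 |
| 95 | 0.963 | 0.929 |
| 100 | 0.970 | 0.940 |
| 104 | 0.974 | 0.948 |
| 105 | 0.975 | 0.950 |

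The minimum for 0.95 is 88 one-sided and 105 two-sided.

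**3. Rounding of the effect size.** The effect size was calculated from earlier data, so 0.50 may be a rounded value. One-sided, the exact minimum is 87 for d of about 0.501 to 0.503. Two-sided, the minimum runs from 108 at d = 0.495 to 103 at d = 0.505. No value that rounds to 0.50 gives 87 two-sided at power 0.95.

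**4. Other tests with the printed inputs.** A paired t-test gives 45 (one-sided) or 54 (two-sided). A rank test with assumed relative efficiency 3/π (normal data) gives 92 or 110. Neither gives 87.

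**5. Entries that give 87 but differ from the printed inputs.**
- Two-sided, power 0.95, d = 0.55: 87, with power 0.972 at 100.
- Two-sided, power 0.90, d about 0.496: 87. At d = 0.500 it is 86.

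**6. The reserve.**
- One-sided: 100 − 88 = 12 per group.
- Two-sided: 100 − 105 = −5 per group.
- Rank test, same efficiency assumption: power at 100 is 0.964 one-sided and 0.930 two-sided.

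**7. The rejection rule at 100 per group (198 df).** Critical t is 1.6526 one-sided and 1.9720 two-sided. Multiplying by √(2/100) = 0.1414 gives observed differences of 0.234 SD and 0.279 SD. A result between these, in favour of the education, is significant only one-sided. If d = 0.50, the probability of landing there is about 0.03.

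**The case against.** The strongest reply is that nothing in the plan says two-sided. That reading rests on a non-directional verb and an unqualified p < 0.05, while the Introduction speaks of improving behaviour and of positive change. This stands to a degree: the defect is an unstated choice, not two explicit statements in conflict. The directional language in the Introduction is background and does not declare a one-sided test.

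A reader might go further and infer that 87 is proven to come from a one-sided run, or that it is an arithmetic slip. The documents support neither. With d at exactly 0.500 the exact one-sided answer is 88, and reaching 87 requires either the normal approximation or an unrounded d slightly above 0.50. The two-sided entries in step 5 of the working also give 87. They contradict a printed input, but a mistyped or misreported entry would do the same. If d was in fact 0.55, the reserve exists and the printed effect size is what needs correcting.

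It can also be said that the effect is small: one percentage point at 100, and about a 3% chance that the two rules disagree if d = 0.50. That is correct and limits the weight of the point. It does not rescue the claim that 100 carries a margin over 0.95 on the two-sided reading.

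Finally, whole class branches are allocated, three per group, so every figure here is optimistic if pupils within a branch resemble one another. That is a separate matter, but it governs how any restated power should be labelled.

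**Conclusion.** The point holds as a lack of specification with a modest numerical consequence. With the printed inputs, 87 fits only a one-sided independent t-test. On the two-sided reading, which the hypothesis and analysis sections suggest without saying so, 105 per group are needed (103 to 108 over the rounding range of d). Power is then about 0.94 at 100 and 0.91 at 87, so 87 is not the minimum for 0.95 and 100 contains no reserve.

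It would be wrong to conclude from this that the trial is seriously underpowered or must enrol more pupils: about 0.94 under the plan's own assumptions is close to target. Nor may 0.94 be read as the trial's actual power. It assumes independent pupils and d = 0.50, and allocation by class branch makes it an upper figure.

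**What to change.** 1. Confirm the G*Power entries (test, tails, effect size, power) and correct the Sample section if any differs from what is printed.
2. State in Sample and in Statistical Analysis that the between-group t-test is two-sided at the 0.05 level.
3. If the entries are as printed, remove 87 as the minimum for 0.95 power, and stop describing the increase to 100 as a reserve above it.
4. Restate power along these lines: *For a standardised difference of 0.50 and a two-sided 0.05 level, power is about 0.94 with 100 analysable pupils per group and about 0.91 with 87. These figures assume independent pupils and are upper figures, because whole class branches are allocated.*

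If a one-sided test was in fact pre-planned, Sample and Statistical Analysis should say so. Power at 100 is then about 0.97 under the same assumptions, and 12 per group remain above 88. The hypothesis should not be made directional merely to fit the number 87.

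The cost is a few sentences and a slightly lower stated power (0.94 instead of 0.95). No extra pupils and no change of design are needed.

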### **Inclusion Criteria**

Being educated in 3rd and 4th grade

Volunteer to participate in the research

Consent of the student's parent

Speak and understand Turkish

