### **Research Groups**

#### **Intervention arm**

Experimental group will be selected from the branches 3rd and 4th grade. 3 branches will be selected for the experimental group. Branches will be determined by drawing. In order not to interfere with the education of students during the training, the groups will be designated as class branches. Students selected for the experimental group will be trained by the researcher for school accidents prepared in line with the components of the Health Belief Model. The training program will be planned as 30 minutes per week for 4 weeks. Before the training and at the end of the training (at the end of the 4th week), the students will be applied personal information form and a behavior scale for safety precautions in school accidents.

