#### **Control Arm**

Control group will be selected from the branches 3rd and 4th grade. 3 branches for the control group. Branches will be determined by drawing. In order not to interfere with the education of students during the training, the groups will be designated as class branches. After the training of the experimental group is completed and the final data are obtained, a 40-minute training will be given to the control group about prevention from school accidents. This training was planned so that the control group would not be devoided of the intervention.

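### Three branches per arm are drawn from two grades with no rule for grade mix, and the t-tests, as stated, include neither grade nor the pretest in the between-group comparison (minor)

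*Combined protocol and SAP*

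**What the plan says.** The allocated units are whole class branches, six in all. The Sample section says "Experimental and control groups will be selected from the branches 3rd and 4th grade" and then "3 branches will be selected for the experimental group and 3 branches for the control group. Branches will be determined by drawing". The arm descriptions repeat the source for each arm separately: "Experimental group will be selected from the branches 3rd and 4th grade" in Intervention arm and "Control group will be selected from the branches 3rd and 4th grade" in Control Arm. Inclusion Criteria admit both grades ("Being educated in 3rd and 4th grade"). No section sets the number of branches per grade in an arm, or stratifies or matches the draw by grade. The number of branches available is not given.

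Study Design states "It has a pretest-posttest design with a control group". Intervention arm times the measurements ("Before the training and at the end of the training (at the end of the 4th week"), and Control Arm lists no pretest of its own. Besides percentages and means, Statistical Analysis gives only "t-test for independent samples and t-test for dependent samples will be used". It names no covariate and does not say which score enters the independent-samples test.

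**The concern.** With only six units allocated, 100 pupils per arm does nothing to average out a factor that varies between classes. If safety behaviour differs between 3rd and 4th grade and the arms receive different grade mixes, part of the observed posttest difference is a grade difference. The planned tests would not show this. The dependent-samples test uses the pretest only within an arm, so it does not correct the comparison between arms. The draw happens once, and an uneven result cannot be fully repaired afterwards, whereas balancing grade beforehand costs almost nothing.

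**Working it through.** **The plan's own figure.** With effect size 0.50 (taken as a standardised mean difference), alpha 0.05 and power 0.95, a one-sided normal calculation gives n = 2 × (1.645 + 1.645)² / 0.50² = 86.6, so 87 per group, as stated in Sample. The two-sided equivalent is 104. Sidedness is a separate matter; 0.50 serves here only as a yardstick.

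**Inputs.** From the documents: three branches per arm, two grades, allocation by drawing, effect size 0.50. Assumed, because the documents are silent: the pool of branches (one grade + the other), the grade gap g in SD units, the pretest-posttest correlation r, and class sizes (equal unless stated).

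**Step 1: how often the arms match.** Let k be the absolute difference between arms in the number of 3rd-grade branches. Counting every free draw:

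| Pool | Draws | k = 0 | k = 1 | k = 2 | k = 3 |
|---|---|---|---|---|---|
| 3+3 | 20 | 0 | 18 (90%) | 0 | 2 (10%) |
| 4+2 | 20 | 12 (60%) | 0 | 8 (40%) | 0 |
| 4+4 | 560 | 144 (26%) | 288 (51%) | 96 (17%) | 32 (6%) |

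If every arm must contain both grades, 3+3 gives k = 1 in 18 of 18 draws, 4+2 gives k = 0 in 12 of 12, and 4+4 gives k = 0 in 144 of 432 and k = 1 in 288 of 432.

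**Step 2: size of the shift.** With equal classes, the shift in an unadjusted posttest comparison is g × k/3.

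- Both grades in each arm: k is 0 or 1. For g = 0.2 the shift is 0 or 0.2/3 = 0.067 SD, and 0.067/0.50 = 13%. For g = 0 there is no shift.
- An arm may hold one grade: for g = 0.2, k = 2 gives 0.133 SD and k = 3 gives 0.20 SD.
- The signed shift averages zero over draws. Its root-mean-square under a free draw is √(mean k²)/3: √1.8/3 = 0.45 of the gap (3+3), √1.6/3 = 0.42 (4+2) and √1.714/3 = 0.44 (4+4).
- For g = 0.2, k = 1, 100 pupils per arm and no training effect, the two-sided false-positive rate given that imbalance is about 0.075 instead of 0.05, ignoring clustering.
- Unequal classes (28 to 38 pupils assumed) move the k = 1 multiplier from 0.33 to between 0.19 and 0.46, and leave up to 0.14 of the gap even when the splits match.

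**Step 3: what pretest adjustment does.** Take a grade gap that is stable over time, k = 1 and within-grade SD 1. The pooled slope is (r + 2g²/9)/(1 + 2g²/9), and the remaining shift is (g/3)(1 − slope), close to (1 − r) of the unadjusted shift. For g = 0.2, the 0.067 SD falls to 0.046, 0.033 or 0.020 SD for r = 0.3, 0.5 or 0.7. Ignoring clustering, two-sided power at 100 per arm rises from 0.942 to 0.960, 0.983 or 0.999.

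**Step 4: cost of fitting grade with arm under 2:1 v 1:2.** The arm-grade correlation is 1/3, so the standard error grows by √(1/(1 − 1/9)) = 1.061. At class level the lost degree of freedom adds to this: (3.182/2.776) × 1.061 = 1.22 without a pretest term, and (4.303/3.182) × 1.061 = 1.43 with one.

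**The case against.** The strongest reply is that the harm rests on quantities the documents do not contain: a grade gap, a branch pool and a correlation. The gap could be zero. That stands, and it limits the point to a precaution.

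The arm descriptions name both grades for each arm, so the natural reading is that each arm contains both. A reader might infer that arm and grade could be completely confounded. That outcome, and the two-branch difference, need the other reading, in which an arm may hold a single grade. The wording does not exclude that reading, but it does not establish it, so those figures should not carry the weight.

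A reader might also infer that an odd number of branches prevents matching. It does not: arms match whenever their splits are the same, for example 2:1 in both. Matching is impossible only for particular pools such as 3+3.

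Nor do the documents show that the pretest is ignored between groups. An independent-samples test on change scores is compatible with the text and would remove a stable grade gap, though not grade-dependent change over the four weeks. What stands is that the plan does not say which score is tested.

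Finally, grade is only part of the variation between branches. With three branches per arm, an assumed intraclass correlation of 0.02 alone gives a class-level SD of the arm difference of √(2 × 0.02/3) = 0.115 SD. That exceeds the 0.08 to 0.09 SD root-mean-square from a 0.2 SD grade gap under a free draw. This is correct, and it means that pretest adjustment must not be taken as dealing with clustering.

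**Conclusion.** The point holds as a minor one. The draw has no rule for grade mix, and the stated analysis has no grade term and no stated between-group use of the pretest. On the natural reading of the arm descriptions, the consequence is a shift of 0 or one third of whatever grade gap exists. That is at most 0.067 SD if the gap is 0.2 SD and classes are equal in size. A reader might call this bias. It is not systematic, because over a symmetric draw the error averages zero; it is a chance error in the single draw that takes place. The pool sizes, the gap and the correlations are all assumptions.

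**What to change.** 1. **Sample, Intervention arm and Control Arm:** draw branches separately within grade so that both arms have the same 2:1 split. This needs at least 4+2 branches; where either grade could supply the pair, draw which one does. If only 3+3 exist, restrict the draw to 2:1 v 1:2, draw which arm gets two 3rd-grade branches, and accept that a one-branch difference remains.
2. **Statistical Analysis:** make the posttest adjusted for the pretest the primary between-group comparison, and confirm that the pretest is given in both arms. Intervention arm schedules it explicitly; for controls it is only implied by Study Design. Clustering by branch is a separate issue, but it must be handled in the same model.
3. **If the splits still differ:** use a joint fit of grade and arm at most as a prespecified sensitivity analysis.

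**Cost.** The draw becomes slightly more complex but stays random: 12 of 20 allocations remain with 4+2, 18 of 20 with 3+3 and 144 of 560 with 4+4. With equal classes it removes the imbalance for 4+2 and 4+4. For 3+3 it only rules out complete separation, and if each arm must already contain both grades it changes nothing for 3+3 or 4+2. The adjustment needs no new data if controls are pretested. The sensitivity analysis has a class-level interval about 22% wider, or 43% with the pretest term, under 2:1 v 1:2, so it will rarely be decisive.
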